## Appendix I: Clinical Protocol Summary of Changes

### Version 4.0, 10 July

2023

Additions to the text are **bolded**, and deletions from the text are ~~crossed off~~. Only the parts of sections with changes are presented. Please note that formatting changes and minor changes to punctuation, spelling, and abbreviations that do not affect meaning are not noted in this summary.

---

#### Section 1.1.2.1 Rationale for Switching to AC176 Tablets and Section 5.1.1 Dose-Escalation (Part A)

The formulation for the investigational product AC176, is switching from a 30 mg capsule to a smaller **30 mg tablet**. The rationale for this decision is described in Section 1.1.2.1, and further details are provided in Section 5.1.1.

---

#### Synopsis and Section 5.0 Study Design

Sections of the Synopsis, Section 5.0 and other applicable areas (e.g., Section 10.1 of the protocol have been modified to include the following **changes**:

Up to **130** patients are planned to be enrolled into this study, from 36 patients.

Backfill and Expansion Cohorts have been added. Up to **approximately 70 patients** are expected to be enrolled in Part A Dose-Escalation plus the Backfill cohorts.

#### Alternative dosing and schedules have been added.

In Part A Dose-Escalation, AC176 will be given orally (PO). The starting dose will be 30 mg and will follow a 3+3 design, see **Figure 1**. **If suggested by emerging safety or PK findings, or as appropriate based on other data from previous cohorts, and approved by the Safety Review Committee (SRC), an alternative dosing level and/or dosing schedule may be considered, which could include twice daily (BID) or intermittent dosing. Alternative dosing schedules may be tested concurrently, provided the total dose is not greater than that of the dose level being evaluated.**

**Prostate cancers with androgen receptor (AR) mutations are more dependent on the AR pathway for their growth. Degradation of AR makes these cancers more susceptible to cell death. Thus, AR-mutated cancers may respond to AR degradation at lower doses than their wildtype counterparts. As more data emerges from Part A, and the tested cohorts are cleared and deemed safe, patients with known AR point mutations may be eligible to enroll in Backfill cohorts. The backfill patients will be enrolled to further characterise the objectives for the study. The total number of patients enrolled in the Backfill cohort will not total more than 12 patients when combined with the number of patients already enrolled in the same cohort. Toxicity for the patients enrolled in a Backfill cohort will be**

*CONFIDENTIAL*

Study Drug: AC176

Sponsor/Development Innovations Study Number: AC176-001/GU 207

Final Protocol: 10 July 2023 Version 4.0

managed according to the Dose Modification Section 6. Up to approximately 70 patients are expected to be enrolled in Part A dose-escalation plus the backfill patients.

The recommended dose for the Expansion cohort will be determined in the Part A Dose-Escalation part of the study. Up to two cohorts may be explored in Part B with approximately 30 patients each. One cohort will be for patients with AR point mutations. The other cohort will be for patients without AR point mutations. The Sponsor and SRC will determine the dose and schedule(s) for the Expansion cohorts based on tolerability and emerging data.

Patients enrolled in Backfill (Part A) and Expansion cohorts (Part B) will be pre-screened for AR mutation status, unless patients can provide documentation that they have the AR point mutation. All Patients will retrospectively undergo central laboratory testing for AR mutation confirmation at Cycle 1 Day 1 per the Schedule of Assessments (SOA).

---

### 3.2 Exclusion Criteria

Patients who meet any of the following criteria will be excluded from study entry:

16. Treatment with any of the following:
  - More than 2 lines of chemotherapy **in the CRPC setting.**

#### Section 5.1.2 Backfill Cohorts

This section provides the details for the Backfill Cohorts, the number of patients to be enrolled, the eligibility requirements, and how the cohorts will be implemented. Also refer to Section 7.2

---

#### Section 5.1.3 Dose-Limiting Toxicity

The following clarification was made:

A toxicity will be considered dose-limiting if it occurs during the first cycle of treatment with AC176 **during the dose-escalation phase (excluding Backfill cohort patients).** Dose-limiting toxicities (DLTs) will not include any toxicity related to underlying disease (including disease progression), intercurrent illness, concomitant medications, or extraneous causes.

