**Table 4 Dose-Escalation (3+3) Design**

Number of Patients with a DLT	Action
0 of 3 patients	Escalate to next dose level
1 of 3 patients	Accrue 3 additional evaluable patients at the current dose level (for a total of up to 6 evaluable patients) a
1 of 6 patients	Escalate to the next dose level
2 or more patients in a dose level group of up to 6 patients	The MTD has been exceeded

DLT = dose-limiting toxicity; MTD = maximum-tolerated dose

a For a patient to be considered “evaluable,” he must have met the minimum safety evaluation requirements of the study, and/or experienced a DLT.

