### 5.1.3 Dose-Limiting Toxicity

Toxicity will be assessed using NCI CTCAE Version 5.0 unless otherwise specified.

A toxicity will be considered dose-limiting if it occurs during the first cycle of treatment with AC176 during the dose-escalation phase (excluding Backfill cohort patients). Dose-limiting toxicities (DLTs) will not include any toxicity related to underlying disease (including disease progression), intercurrent illness, concomitant medications, or extraneous causes. DLTs will be defined as follows:

- Any Grade 5 toxicity
- **Hematologic:**
  - Grade 4 neutrophil count decrease for >7 days; or febrile with neutrophil count decrease (ANC <1000/mm^3 with a single temperature of >38.3°C [101°F] or a sustained temperature of ≥ 38°C [100.4°F] for more than 1 hour)
  - Grade 4 platelet count decrease; or Grade 3 platelet count decrease associated with clinically significant bleeding, including any bleeding that warrants a platelet transfusion, related to drug
  - Grade 4 anemia related to drug (life-threatening consequences requiring urgent interventions)
- **Non-Hematologic:**
  - Grade 3 or 4 non-hematologic toxicity, with the **exception of**:
    - Alopecia;
    - Grade 3 nausea, vomiting, or diarrhea if well-controlled by supportive care within 72 hours;
    - Grade 3 skin rash that improves in ≤7 days, with or without supportive care;
    - Grade 3 fatigue that improves in ≤7 days, with or without supportive care;
    - Grade 3 endocrinopathies that only require treatment with hormone replacement therapy;

*CONFIDENTIAL*

Study Drug: AC176

Sponsor/Development Innovations Study Number: AC176-001/GU 207

Final Protocol: 10 July 2023 Version 4.0

- Grade 3 non-hematologic laboratory abnormalities, other than liver function tests, will not be considered a DLT unless they are associated with clinical manifestations which lead to medical intervention and/or hospitalization.
- Potential drug-induced liver injury consistent with Hy's Law (Appendix F), defined as AST and/or ALT  $>3 \times$  ULN with concurrent total bilirubin  $>2 \times$  ULN without findings of cholestasis (alkaline phosphatase [ALP]  $>2 \times$  ULN)
- Grade 3 or higher electrolyte abnormality that lasts  $>72$  hours, unless the patient has clinical symptoms, in which case all Grade 3 or higher electrolyte abnormalities regardless of duration should count as a DLT

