### **Determination of Dose-Limiting Toxicities**

The patient population used for determination of DLTs will consist of patients who have met the minimum safety evaluation requirements of the study, and/or who have experienced a DLT. Minimum safety requirements will be met if, during Cycle 1 of treatment, the patient receives at least 75% of planned total doses of AC176 and is observed for at least one cycle following the first dose of AC176. The minimum safety requirements must be met for a patient to be included in the MTD-determining population.

Patients who discontinue treatment early due to disease progression or withdrawal will be asked to have all end-of-treatment (EOT) safety evaluations performed as described in the protocol (see Section 7.6). If a patient withdraws from treatment during Cycle 1 due to any reason other than a DLT and does not meet the minimum requirements for inclusion in the MTD-determining population described above, that patient will be replaced.

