### **11.1.4 Suspected Adverse Reaction**

Suspected adverse reaction (SAR) means any AE for which there is a reasonable possibility that the drug caused the AE. "Reasonable possibility" means that there is evidence to suggest a causal relationship between the drug and the AE. An SAR implies a lesser degree of certainty about causality than adverse reaction, which means any AE caused by a drug.

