#### **11.1.6 Assessment of Adverse Events**

All AEs and SAEs, whether volunteered by the patient, discovered by study personnel during questioning, or detected through physical examination, laboratory test, or other means, will be reported appropriately. Each reported AE or SAE will be described by its duration (i.e., start and end dates), regulatory seriousness criteria if applicable, suspected relationship to the study drug (see following guidance), and actions taken.

To ensure consistency of AE and SAE causality assessments, Investigators should apply the following general guideline:

**YES:** There is a plausible temporal relationship between the onset of the AE and administration of the study treatment, and the AE cannot be readily explained by the patient's clinical state, intercurrent illness, or concomitant therapies, and/or the AE follows a known pattern of response to the study drug, and/or the AE abates or resolves upon discontinuation of the study drug or dose reduction and, if applicable, reappears upon re-challenge.

**NO:** Evidence exists that the AE has an etiology other than the study drug (e.g., pre-existing medical condition, underlying disease, intercurrent illness, or concomitant medication), and/or the AE has no plausible temporal relationship to study drug administration (e.g., cancer diagnosed 2 days after first dose of study drug).

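### The DLT exclusion in Section 5.1.3 is not limited to toxicities clearly and solely due to another cause, so a Cycle 1 event to which AC176 may also have contributed can go uncounted in the 3+3

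*Protocol*

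**What the plan says.** Section 5.1.3 opens its DLT definition with an attribution exclusion: "Dose-limiting toxicities (DLTs) will not include any toxicity related to underlying disease (including disease progression), intercurrent illness, concomitant medications, or extraneous causes". The trigger is a relation to one of those causes. Two of the hematologic criteria that follow carry their own wording on drug-relatedness, for example "Grade 4 anemia related to drug (life-threatening consequences requiring urgent interventions".

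Attribution of AEs in general is set elsewhere:

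- Section 11.1.4 defines a suspected adverse reaction as "any AE for which there is a reasonable possibility that the drug caused the AE".
- Section 11.1.6 offers only YES or NO. The YES conditions are linked by and/or, and one of them is that "the AE abates or resolves upon discontinuation of the study drug or dose reduction and, if applicable, reappears upon re-challenge". NO applies where there is evidence of a different etiology, with disease, intercurrent illness and concomitant medication among the examples.

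The count feeds Table 4. With one DLT in three patients the action is "Accrue 3 additional evaluable patients at the current dose level"; 0/3 and 1/6 lead to escalation; "2 or more patients in a dose level group of up to 6 patients" means that the MTD has been exceeded. Section 5.1.4 defines the MTD on the same count.

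**The concern.** DLTs are the first-listed primary endpoint and drive both Table 4 and the MTD. The exclusion does not say what happens when two causes are plausible. Take a Grade 4 anemia in Cycle 1 to which marrow disease and AC176 may both have contributed. It can be scored as a DLT under its own criterion and left out under the opening sentence of the same section. Under 11.1.6 it can fit the YES text (it resolved when the drug was held) and also the NO text (another etiology is in evidence), and no tie-break is given. Two sites could score the same event differently. An event listed as treatment-related in the AE tables could be absent from the DLT count.

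Cohorts are so small that one event decides the action. A level cleared with one event missing may then open to backfill (up to 12 patients in total, Section 5.1.2) and to intra-patient escalation (Section 5.1.5), and the MTD is the ceiling for the RP2D (Section 5.1.6).

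**Working it through.** **Inputs from the protocol.** Table 4: 0/3 escalate; 1/3 add three; 1/6 escalate; 2 or more in up to 6 stop. Section 5.1.4: MTD is the highest dose with at most 1 of 6.

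**Inputs assumed.** The protocol gives no target DLT rate and no operating characteristics, so there is no stated figure to reproduce on this point. Let p be the true DLT rate and f the share of true DLTs left uncounted because another cause also played a part. Neither is in the document; ranges are shown.

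**Formulas.** Counted rate q = p(1 − f).

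P(level cleared by count) = (1 − q)³ + 3q(1 − q)² × (1 − q)³ = (1 − q)³ + 3q(1 − q)⁵.

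P(at most 1 DLT in 6) = (1 − q)⁶ + 6q(1 − q)⁵.

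**Worked case, p = 0.40.**

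- f = 0: q = 0.40; 0.216 + 1.2 × 0.07776 = 0.309
- f = 0.10: q = 0.36; 0.2621 + 1.08 × 0.1074 = 0.378
- f = 0.25: q = 0.30; 0.343 + 0.9 × 0.16807 = 0.494
- f = 0.50: q = 0.20; 0.512 + 0.6 × 0.32768 = 0.709

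**Range, P(level cleared by count).**

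| p | f = 0 | f = 0.10 | f = 0.25 | f = 0.50 |
|---|---|---|---|---|
| 0.33 | 0.43 | 0.50 | 0.61 | 0.78 |
| 0.40 | 0.31 | 0.38 | 0.49 | 0.71 |
| 0.50 | 0.17 | 0.23 | 0.35 | 0.60 |

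P(at most 1 of 6) at p = 0.40 is 0.23, 0.30, 0.42 and 0.66 across the same values of f.

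**Sensitivity to replacement.** The table treats a patient with an uncounted event as evaluable and DLT-free. The subsection on determining DLTs also provides for replacement: "If a patient withdraws from treatment during Cycle 1 due to any reason other than a DLT" and the patient lacks the minimum exposure or observation, another is enrolled. If every such patient were replaced, the counted rate would be p(1 − f)/(1 − pf). At p = 0.40 this gives 0.36/0.96 = 0.375, 0.30/0.90 = 0.333 and 0.20/0.80 = 0.25 for f = 0.10, 0.25 and 0.50. P(cleared) is then 0.244 + 1.125 × 0.0954 = 0.35, 0.296 + 1 × 0.132 = 0.43 and 0.422 + 0.75 × 0.237 = 0.60. The increase is smaller but in the same direction.

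**The text side by side.** Section 11.3.4 handles deaths due only to disease progression separately and uses sole-cause wording to do so. The protocol therefore draws that distinction where it wants it, but the DLT exclusion does not use it.

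**The case against.** The best reply is that *related* is a two-way attribution in this protocol. Section 11.1.5 asks the investigator whether an event is related or unrelated, and the causes listed in 5.1.3 closely follow the examples under NO in 11.1.6. On that reading the exclusion removes only events attributed elsewhere, which is close to the intended rule. This is a fair reading, and it shows that the text is silent on mixed causes. A reader might infer that the protocol orders such events to be dropped; no sentence says so. The silence remains, because a mixed-cause event can fit both YES and NO.

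Several stronger inferences also fail:

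- *5.1.3 flatly contradicts 11.1.4.* Section 11.1.4 defines a term for safety reporting, and DLT scoring may use a different standard. The first YES limb of 11.1.6 itself asks that the event not be readily explained otherwise. The difficulty is an unreconciled overlap.
- *All error in the DLT definition runs towards too few DLTs.* Grade 5 toxicity, prolonged Grade 4 neutrophil decrease and the main Grade 3/4 non-hematologic criterion need no positive finding of drug-relatedness. Events of unclear cause count by default, which is conservative. Only the mixed-cause gap works downwards.
- *A too-toxic level will be cleared.* Escalation also weighs the safety profile and PK data (Section 5.1.1), and the SRC reviews all available safety data and may expand, de-escalate or stop (Section 10.5.3). An uncounted event stays visible there. But neither section says how to attribute an event for the count, and Table 4 and the MTD still rest on the count.

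How often mixed causes would arise is not documented. Eligibility limits on blood counts, liver tests and performance status would reduce it.

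**Conclusion.** The point holds as a gap in a stated rule of the primary endpoint. As written, 5.1.3 permits a Cycle 1 toxicity with a possible AC176 contribution to go uncounted, and this raises the chance that Table 4 clears a level that is too toxic.

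The direction follows from the rule; the size depends on assumed values. At an assumed true rate of 40%, the chance of clearing by count goes from 31% to 38%, 49% or 71% with 10%, 25% or 50% of true DLTs uncounted (35%, 43% or 60% if all those patients are replaced). The upper figures need half of all true DLTs to be lost and the SRC to add nothing, so they are a bound for illustration and not a forecast. The documents do not support saying that such events are certain to disappear or that an unsafe dose is certain to pass.

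A statistical analysis plan is not the natural home for the remedy, because DLTs are scored cohort by cohort while escalation is under way.

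**What to change.** Reconcile 5.1.3 with 11.1.6 by stating one attribution standard for DLTs. In 5.1.3, replace the exclusion with wording to this effect: *a toxicity meeting the criteria below is excluded only when it is clearly and solely attributable to a documented cause other than AC176; if AC176 may also have contributed, it counts.* Say that the same standard governs the drug-relatedness wording in the hematologic criteria.

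Limit this to DLT scoring. Causality coding of other AEs under 11.1.6 should stay as it is; a general rule that YES prevails would alter attribution for every AE in the trial and is not needed here.

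Cost: one sentence, through a protocol amendment. A few mixed-cause events will count, so a level may be expanded to 6 or escalation may stop slightly earlier.

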#### Determination of Dose-Limiting Toxicities

The following statement was added to this section: **The minimum safety requirements must be met for a patient to be included in the MTD-determining population.**

---

#### Section 5.1.5 Intra-Patient Dose Adjustment

The following clarifications were made:

Patients may be permitted an intra-patient dose-escalation of AC176 to a higher dose level that has been cleared and deemed safe by the SRC if they have completed at least 2 cycles at their assigned dose level and continued on study with no  $\geq$  Grade 2 treatment-related AEs. The highest dose the patient can be escalated to is the **highest** dose level that **has been cleared for DLT** and is considered to be safe for this patient by the Investigator. The Investigator must consult with the Medical Monitor to confirm that the patient **has been tolerating their AC176 dose.** The patient data will continue to be collected for evaluation of safety and clinical activity,

*CONFIDENTIAL*

Study Drug: AC176

Sponsor/Development Innovations Study Number: AC176-001/GU 207

Final Protocol: 10 July 2023 Version 4.0

and all assessments will continue according to the Schedule of Assessments (see applicable SOA Table 1 or Appendix H).

---

### **Section 5.1.7 Expansion Cohorts (Part B)**

This section provides the details for the Expansion Cohorts, the number of patients to be enrolled, the eligibility requirements, and how the cohorts will be implemented. Also refer to Section 7.2

---

### **Section 7.1 Overview**

The key procedures required in this study include:

- Immature platelet fraction testing (blood based), at sites with the capability, and if clinically indicated**

---

### **Section 7.2 Pre-Screening AR Mutation Status for Backfill Patients and Expansion Cohorts**

**Prostate cancers with AR mutations are more dependent on the AR pathway for their growth. Degradation of AR makes these cancers more susceptible to cell death. Thus, AR-mutated cancers may respond to AR degradation at lower doses than their wildtype counterparts.**

**Pre-screening for AR mutation status is required in the Backfill and Expansion cohorts. If patients provide historic ctDNA testing results of a positive AR point mutation, then pre-screening ctDNA testing for AR mutation status by ctDNA testing is not needed. All patients will retrospectively undergo central laboratory testing for AR mutation confirmation at Cycle 1 Day 1 per the SOA.**

**Patients who have not had AR point mutation testing must agree to sign a pre-screening ICF to collect a blood sample for ctDNA. Confirmation of the AR point mutation does not guarantee eligibility for a backfill cohort or the expansion cohort.**

**Depending on the AR point mutation status, patients may proceed with further screening procedures for Backfill or Expansion cohorts, as appropriate, after signing a separate ICF for the study.**

---

### **Section 7.5.3 Extended Follow-Up Period**

The following clarification has been added:

**If treatment was discontinued for reasons other than disease progression, additional follow-up visits after the 30-day safety follow-up visit will be performed for tumor assessment by imaging as on treatment until PD or another withdrawal criterion is met.**

---

### **Section 7.7 Pharmacokinetic Assessments**

The following has been added to this section:

**Meal consumption prior to PK collections will be collected.**

**If the sample cannot be collected at the visit as scheduled, it should be collected at the next visit whenever possible. Additional unscheduled PK samples may be drawn during the**

*CONFIDENTIAL*

Study Drug: AC176

Sponsor/Development Innovations Study Number: AC176-001/GU 207

Final Protocol: 10 July 2023 Version 4.0

**study if it is deemed clinically indicated for the patient and/or based on newly emerged data from clinical studies of AC176. Similarly, if any PK time point is later deemed unnecessary per acquired clinical PK data, such time point may be removed from PK schedule by the Sponsor.**

---

### **Section 7.8.2 Biomarker Blood Samples**

This section has been revised as follows:

Blood samples for ctDNA will be taken **at pre-screening, if applicable, on Cycle 1 Day 1, and on Cycle 2 Day 1, Cycle 5 Day 1, and Cycle 8 Day 1, and at the EOT visit.** Blood samples for ARv7 will be collected pre-dose on Cycle 1 Day 1 **and at the EOT visit.** Instructions regarding sample collection, handling/processing, and shipping are provided in the Laboratory Manual.

**A blood sample for ctDNA will be required at pre-screening for patients enrolling in Backfill and Expansion cohorts without AR point mutation documentation. The separate pre-screen ICF must be signed by the patient prior to collection of the pre-screening ctDNA sample (see Section 7.2).**

**In addition to the biomarkers listed above, other biomarkers deemed relevant to gain further knowledge about the biology of the disease or about the study drug may be assayed, based on newly emerging data from the study and/or literature data. For similar reasons, unscheduled sampling may be allowed if deemed clinically relevant.**

---

